8.3.2 Histological outcomes

Collagenous colitis (CC)

- Histological remission:

- a) Normal thickness of subepithelial collagen layer ($\leq 5 \mu\text{m}$)³⁹, **and**
- b) No/mild lamina propria inflammation (Geboes grade < 3.1)⁴⁰

Lymphocytic colitis (LC)

Histological remission:

- a) Reduction in the number of IEL ≤ 20 IEL/100 surface epithelial cells⁴¹ **and**
- b) No/mild lamina propria inflammation (Geboes grade < 3.1)⁴⁰

Incomplete colitis (IC)

- Histological remission:¹

- a) Normal IEL (≤ 5 IEL/100 surface epithelial cells) **and**
- b) Normal thickness of subepithelial collagen layer ($\leq 5 \mu\text{m}$), **and**
- c) No/mild lamina propria inflammation (Geboes grade < 3.1)⁴⁰

Histological activity includes (for all subtypes):

- No change in histological features since diagnosis

- a) No change in lamina propria inflammation (Geboes grade ≥ 3.1)
- b) No change in collagen layer thickness, and
- c) No change in number of IELs in the surface epithelium.

None of these parameters show any increase in any segment assessed.

- Histological aggravation since diagnosis

- a) Any increase in any segment in lamina propria inflammation (Geboes grade ≥ 3.1),
- b) Any increase in collagen layer thickness, **and/or**
- c) Any increase in number of IELs in the surface epithelium.

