- Result of colonoscopy: normal/abnormal - describe whether other findings may have caused diarrhoea (e.g., polyps > 2 cm, tumors, Crohn's disease, ulcerative colitis, ischemic colitis, other).

For patients with macroscopically normal colonoscopy:

- Date of sampling of colonic specimens (this date will correspond to the date of MC diagnosis, if confirmed).
- Date of histological assessment
- Histological evidence of MC (yes/no). The following features will be captured:
 - Geboes Index (grade for each of the colon segments: rectum, sigmoid, descending, transverse and ascending) – see Section 7.4.2.
 - Thickness of the subepithelial collagen layer (not observed, $\leq 5 \mu\text{m}$; > 5 and $< 10 \mu\text{m}$; $\geq 10 \mu\text{m}$)
 - IEL in the surface epithelium (not observed, < 5 IEL/100 surface epithelial cells, > 5 and < 20 IEL/100 surface epithelial cells, ≥ 20 IEL/100 surface epithelial cells);
- If a diagnosis of MC was not confirmed, was other diagnosis established? Yes/no - if yes, describe.

Characterization of MC patients

- MC histological assessment: location of microscopic findings (by colon segment), type of MC (lymphocytic, collagenous, incomplete colitis) - see histological assessment in section 7.4.
- Therapeutic attitude upon MC confirmation
 - Antidiarrheal medication (e.g., loperamide or diphenoxylate/atropine),
 - Bismuth subsalicylate or aminosalicylates, e.g. 5-aminosalicylic acid
 - Cholestyramine
 - Corticosteroids (budesonide, prednisolone)
 - Immunosuppressive agents, e.g. azathioprine, 6-mercaptopurine or methotrexate
 - Surgical intervention (e.g. ileostomy)
 - Other interventions (pharmacological or non-pharmacological)
- Dispensing of patient diary card to document the number of stools including the type according to Bristol stool form scale (see section 7.2) in the week prior to the next appointment. In addition, the use of additional pharmacological or other therapies will be recorded by the patient.

Follow up assessments of MC patients (as per routine practice) - month 3, 6, 9, 12, 15, 18, 21 and 24.

The following will be assessed throughout the 24-month prospective component of the study - see **Appendix**.

At every data collection time point

- Weight (kg)
- Symptoms (to be captured by the physician by checking the patient diary and interviewing the patient, referring to the previous 7 days):

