 - number of stools per day (the mean number of stools and watery stools per day will be calculated by summing the number of stools [any type] and watery stool that occurred over the week before the time point of assessment divided by 7 days).
 - type of stool (1 to 7 - Bristol Stool Chart)
 - nightly diarrhea
 - urgency (0 = no urgency, 1 = need to defecate within 30 minutes, 2=immediate need to empty the bowel, 3 = fecal incontinence - have to go immediately to the toilette)

- difficulties staying continent with a respective bowel movement
- abdominal pain (0 = no pain, 1 = mild, 2 = moderate, 3 = severe pain)
- Laboratory parameters – hemoglobin, platelets, leukocytes, neutrophils, eosinophiles, basophiles, monocytes, lymphocytes, erythrocyte sedimentation rate (ESR), C-reactive protein (CRP), iron and transferrin.
- Concomitant medications
- Changes in concomitant illness (worsening of previous conditions, new condition)

At diagnosis of MC and every 3 months up to month 24:

- Fecal sample – for assessment of calprotectin, ECP and EPX levels.

In addition, at Month 24 only:

- Date of colonoscopy with sampling of colonic specimens
- Result of colonoscopy: normal/abnormal - describe
- Date and result of histological assessment :
 - Geboes Index (grade for each of the colon segments: rectum, sigmoid, descending, transverse and ascending) – see Section 7.4.2.
 - IEL in the surface epithelium (not observed, < 5 IEL/100 surface epithelial cells, > 5 and < 20 IEL/100 surface epithelial cells, ≥20 IEL/100);
 - Thickness of the subepithelial collagen layer (not observed, <5 µm; > 5 and < 10 µm; ≥ 10 µm).

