8.2 SECONDARY ENDPOINTS

- Proportion of patients with confirmed diagnosis of each subtype of MC (CC, LC and IC)
- Age, gender, BMI, smoking status, duration of symptoms, stool frequency and consistency (type), familial history of IBDs, comorbidities, previous pharmacological/ non-pharmacological therapies and laboratory parameters to be compared between MC patients and non-MC patients.
- Treatments (pharmacological/non-pharmacological) prescribed by specialist for patients with MC diagnosis
- Number of stools and type (Bristol stool form scale), urgency and abdominal pain over the last 7 days before each time point of assessment for patients with MC diagnosis.
- Proportion of MC patients with clinical remission at each data collection time point (month 3, 6, 9, 12, 15, 18, 21 and 24)
Clinical remission: mean of < 3 stools per day and mean of < 1 watery stool per day
- Proportion of MC patients with histological remission at month 24.
See section 8.3.2 for definition of histological remission
- Age, gender, BMI, smoking status, duration of symptoms, stool frequency and consistency, familial history of IBDs, age at diagnosis of MC, time to diagnosis of MC, comorbidities, pharmacological/non-pharmacological therapies, laboratory parameters and histological features, compared with clinical activity status (active/non active) described for patients with MC diagnosis.
- Age, gender, BMI, smoking status, duration of symptoms, stool frequency and consistency, familial history of IBDs, age at diagnosis of MC, time to diagnosis of MC, comorbidities, pharmacological/non-pharmacological therapies, laboratory parameters, compared with histological features, described for patients with MC diagnosis.
- Area under the ROC curve of fecal calprotectin, ECP and EPX levels with clinical activity at each data collection time points among MC patients.
- Area under the ROC curve of fecal calprotectin ECP and EPX levels with histological activity at each data collection time points among MC patients

For definition of clinical and histological activity see section 8.3.1 and 8.3.2.

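### Histological activity (section 8.3.2) is not the complement of remission, and the bands listed in section 7.1 cannot fully support it, so the exploratory activity endpoint lacks a usable binary status

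*Protocol*

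**What the plan says.** Section 3.2 sets three exploratory objectives on histological activity: its relation to patient characteristics, to treatments and to faecal markers. Section 8.2 adds the endpoint "Area under the ROC curve of fecal calprotectin ECP and EPX levels with histological activity at each data collection time points among MC patients" and directs the reader on: "For definition of clinical and histological activity see section 8.3.1 and 8.3.2". Section 9.1 uses the AUC to relate numerical variables to binary ones.

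In section 8.3.2, remission is an absolute state, and each subtype also needs Geboes < 3.1:
- CC: collagen ≤ 5 µm.
- LC: IEL reduced to ≤ 20 per 100.
- Incomplete colitis (IC): collagen ≤ 5 µm and IEL ≤ 5 per 100.

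Activity, for all subtypes, is relative to diagnosis and has two limbs:
- No change in Geboes, collagen and IEL ("No change in number of IELs in the surface epithelium"), with the rider "None of these parameters show any increase in any segment assessed".
- Aggravation, meaning a rise in Geboes, collagen and/or IEL ("Any increase in number of IELs in the surface epithelium").

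Section 7.1 lists the histology to be captured. IEL appears in bands at both times: "IEL in the surface epithelium (not observed, < 5 IEL/100 surface epithelial cells, > 5 and < 20", then ≥ 20. Collagen is banded too. Its lowest measured band is ≤ 5 µm at baseline, but the Month 24 list reads "Thickness of the subepithelial collagen layer (not observed, <5". Geboes is listed for each of five segments; the collagen and IEL bands carry no segment. Section 12.2 sends all study data to the eCRF.

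**The concern.** Section 8.3.1 makes clinical activity and clinical remission exact complements, so every evaluable patient gets exactly one status. Section 8.3.2 does not do the same for histology. It sets a threshold rule beside a change rule, and nothing ensures that the two meet without gap or overlap.

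An AUC, or any comparison of active with non-active patients, needs each patient in exactly one group. Otherwise the analyst must place the remaining patients after seeing the data. In a sample of about 30, a few such placements can move an AUC across the 0.75 mark that section 9.1 treats as high discrimination. The captured variables matter for a second reason: an analysis plan can repair a definition, but it cannot recover measurements that were only ever entered as bands.

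**Working it through.** **The plan's own figure.** Section 9.2 expects 300 × 0.10 = 30 MC patients, as stated. At the upper prevalence it would be 300 × 0.15 = 45.

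**Step 1: do remission and activity partition patients?** Apply section 8.3.2 to measured values, with Geboes < 3.1 and unchanged. The values are illustrative.

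| Subtype | Collagen, µm | IEL/100 | Remission | Activity | Status |
|---|---|---|---|---|---|
| CC | 15 → 8 | 10 → 10 | no (8 > 5) | no (fell, nothing rose) | neither |
| LC | 3 → 3 | 40 → 25 | no (25 > 20) | no (fell, nothing rose) | neither |
| IC | 9 → 7 | 8 → 8 | no (7 > 5) | no (fell, nothing rose) | neither |
| LC | 3 → 6 | 30 → 15 | yes (collagen not considered) | yes (collagen rose) | both |
| CC | 15 → 4 | 8 → 12 | yes (IEL not considered) | yes (IEL rose) | both |
| IC | 7 → 3 | 3 → 5 | yes (both ≤ 5) | yes (IEL rose) | both |

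Enumerating a grid (collagen 3, 5, 7, 9, 12, 16, 20; IEL 3, 5, 8, 15, 20, 25, 40; Geboes below or at/above 3.1; one segment) finds both faults in every subtype. Counts of neither / both are 1134 / 252 of 4116 pairs for CC, 236 / 504 of 2352 for LC and 169 / 16 of 2352 for IC. These counts show that the gaps and overlaps exist. They do not estimate how often patients fall into them.

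**Step 2: unchanged disease.** The no-change limb carries Geboes ≥ 3.1 in brackets. If that is a condition, a CC patient unchanged at 15 µm with Geboes < 3.1 is also neither. If it is only descriptive, the patient is active. The text does not say which.

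**Step 3: time points.** Section 8.2 asks for the activity AUC at each data collection time point. The Appendix schedules histology at baseline and Month 24 only, and a change since diagnosis has no value at diagnosis. That leaves Month 24. Replacing the rule by the complement of remission does not create an AUC at diagnosis. By section 7.4.2, CC has collagen ≥ 10 µm, LC has IEL ≥ 20, and IC has collagen and/or IEL > 5. Practically all MC patients are then active, and there is no comparison group.

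**Step 4: can the listed variables support the definition?**
- Within a band: CC collagen 20 → 11, 12 → 12 and 12 → 20 µm are all recorded as ≥ 10 at both times. Under section 8.3.2 they are respectively neither, no change and aggravation. LC has the same problem in the IEL ≥ 20 band. These top bands define CC and LC.
- At 5: IEL of exactly 5 has no band at either time. Collagen of exactly 5 µm has one at baseline (≤ 5) and none at Month 24 (< 5).
- At 20: IEL of 20 qualifies for LC diagnosis (≥ 20, section 7.4.2), satisfies the LC remission limit if reached by a reduction (≤ 20, section 8.3.2), and is stored in the same band as 25 or 40.
- By segment: section 9.1 wants histological remission by colonic segment, but the Month 24 list gives segments for Geboes only.
- Derivable as listed: Geboes changes by segment, and collagen or IEL rises that cross a band.

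**Size.** Each patient with no status or two is 1/30 = 3.3% of the expected sample (1/45 = 2.2% at 15% prevalence).

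**The case against.** The strongest defence has four parts.

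- **Section 9.1 does not use the activity status.** It sets the markers against three dichotomised features (collagen and IEL at 5, Geboes at 3.1) at diagnosis and Month 24. This stands: those AUCs are computable apart from values of exactly 5. A reader might infer that no marker–histology analysis can be run; the document does not support that. What remains is that sections 8.2 and 9.1 name different outcomes.
- **The eCRF is not shown.** Section 7.4.2 requires the values used for evaluation to be marked, so the pathologist may hold measurements by segment. This is fair, and one cannot conclude that they are lost. But section 7.1 lists bands, and nothing says that measurements enter the database.
- **The Month 24 limit of < 5 µm may be a slip.** Sections 7.4.2, 8.3.2 and 9.1 all place 5 in the normal group. That is plausible, and it is a reason to correct the line.
- **Section 8.3.2 introduces activity as an open list.** Partial improvement might therefore be meant to count as active. The text never says so, and an open list would not remove the overlap.

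A reader might also infer that, because a rise in one segment is enough, reading noise would mislabel most stable patients. The document does not support this. No change and aggravation both count as activity (taking the bracketed Geboes grade as descriptive), so moving a stable patient between them leaves the status as it was. Section 8.2 has no separate aggravation endpoint, and the variable lists do not provide segment-by-segment comparisons of collagen and IEL. Noise could matter for patients in remission or partly improved, but the document gives no basis for a figure. The one-segment trigger is a design choice, not an error.

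**Conclusion.** The point holds within these limits. As written, section 8.3.2 gives some patients no histological status and others two, and gives none at diagnosis. The variables listed in section 7.1 cannot fully support the definition, because of changes within a band and the limits at 5 and 20. The section 8.2 activity AUC and the activity objectives of section 3.2 therefore cannot be computed uniquely.

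The reach is modest. These are exploratory analyses in about 30 patients, and no research hypothesis is set. The primary prevalence endpoint and the sample size do not use the activity definition. Month 24 remission has its own definition and is touched only at the boundary values and in the by-segment summary. The number of patients affected is unknown, because the protocol gives no rate of partial improvement or mixed change. The conclusion on captured data assumes that the eCRF follows section 7.1.

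**What to change.** 1. In section 8.3.2, define histological activity at Month 24 as the strict complement of histological remission. Partial improvement and mixed change then each get one status.
2. Reconcile the LC limit at 20 between sections 7.1, 7.4.2 and 8.3.2, so that one value cannot meet both the diagnostic and the remission limit.
3. Use the same gap-free bands for collagen and IEL at baseline and Month 24, so that 5 has a place at both times.
4. Enter the measured µm and IEL/100 for each segment in the eCRF at both times and derive the bands from them. If aggravation is reported separately, derive it from the measured values, since bands cannot show worsening in the top class.
5. Reconcile section 8.2 with section 9.1: limit the activity AUC to Month 24 and keep the feature-level AUCs at diagnosis and Month 24.

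The cost is text in sections 7.1, 7.4.2, 8.2 and 8.3.2, plus 5 segments × 2 measures = 10 numeric fields per histology assessment. No extra biopsies are needed, and section 7.4.2 already has the pathologist evaluate each segment. The fields must be set before data entry, because bands cannot be turned back into measurements.

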9 STATISTICAL ANALYSIS

9.1 GENERAL CONSIDERATIONS

All quantitative variables will be summarized through descriptive statistics namely mean, median, standard deviation and range (minimum and maximum) and qualitative variables through absolute (n)

and relative frequencies (%) and 95% confidence intervals (if applicable). The statistical analysis will be performed through frequency tables for qualitative variables and tables with descriptive statistics for quantitative variables.

The association between two quantitative variables will be performed through Pearson correlation coefficient or Spearman correlation coefficient, in case the normality assumption is not verified.

The association of two categorical variables will be tested through the Chi-Square test or Fisher Exact test (if applicable).

The comparison of two independent samples in respect to quantitative variables will be performed through t-test for independent samples or the Mann-Whitney non-parametric test, according to the assumption validations of the statistical test (if applicable).

The proportion of patients with clinical remission and histological remission (overall, by MC subtype and colonic segment) at each data collection time points will be summarized using 95% confidence intervals.

Area under the ROC curve will be used to correlate numerical variables with binary categorical variables. A high discriminatory ability will be considered for values > 0.75 .

Repeated Measures Analysis or Generalized Estimated Equations will be used to investigate the evolution profile of clinical and histological characteristics throughout the data collection time points (time-effect).

Generalized Estimated Equations will be used to explore the association between clinical (as independent variable) and histologic features (as dependent variable) observed within-patients.

The association analysis of fecal calprotectin, EPC and EPX with clinical activity

- The association between fecal calprotectin levels EPC and EPX with clinical activity (remission/active disease) will be analyzed through Area Under the ROC Curve at each data collection time point (diagnosis and every 3 months up to month 24).

The association analysis of fecal calprotectin EPC and EPX with histological features

- The association between fecal calprotectin, EPC and EPX levels with histological features (collagen thickness [$\leq 5 \mu\text{m}$; $> 5 \mu\text{m}$], inflammation [Geboes grade < 3.1 ; grade ≥ 3.1] and IEL count [$\leq 5 \text{ IEL}/100$; $> 5 \text{ IEL}/100$ surface epithelial cells) will be analyzed through Area Under the ROC Curve at each data collection time point (diagnosis and month 24).

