3.2 SECONDARY OBJECTIVES

- To determine the prevalence of MC subtypes (CC, LC and IC)
- To compare the socio-demographic, clinical and histological characteristics and previous therapies of patients with confirmed diagnosis of MC (MC patients) versus patients without diagnosis of MC (non-MC patients)
- To describe the therapeutic attitude regarding MC patients over a period of 24 months
- To describe the clinical activity of MC patients over a period of 24 months.
- To describe the histological features of MC patients 24 months after diagnosis.
- To explore the association of socio-demographic, clinical and histological characteristics with clinical activity among MC patients followed for 24 months.
- To explore the association of socio-demographic, clinical characteristics with histological activity among MC patients followed for 24 months.
- To explore the correlation between the treatments used by MC patients and clinical activity.
- To explore the correlation between the treatments used by MC patients and histological activity.

- To explore the correlation between fecal calprotectin, EPC and EPX levels and clinical activity among MC patients.
- To explore the correlation between fecal calprotectin, EPC and EPX levels and histological activity among MC patients.

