9.2 SAMPLE SIZE

This study will include 300 patients with chronic diarrhea allowing the estimation of a prevalence of 10-15%^{23,37} with an error margin of less than 4.5% and with 95% confidence interval. Assuming the lowest rate of the prevalence interval (10%), approximately 30 patients with MC are expected to be followed in the prospective component study.

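### Section 9.1 offers only independent-record methods for relating patient characteristics to clinical activity, although activity is determined at eight follow-up visits in about 30 MC patients

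*Protocol*

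**What the plan says.** - **Objective (Protocol 3.2):** "To explore the association of socio-demographic, clinical and histological characteristics with clinical activity among MC patients followed for 24 months". No visit is singled out.
- **Endpoint (Protocol 8.2):** a list of characteristics (age, gender, BMI, smoking, comorbidities, therapies, laboratory values and others) is to be "compared with clinical activity status (active/non active) described for patients with MC diagnosis".
- **Outcome (Protocol 8.3.1):** activity and remission are defined from stool counts in the week before an assessment, so each visit yields its own status. The companion endpoint in 8.2 lists the visits: "Proportion of MC patients with clinical remission at each data collection time point (month 3, 6, 9, 12, 15, 18, 21 and 24").
- **Methods (Protocol 9.1):** tests are given by type of variable. For two categorical variables: "The association of two categorical variables will be tested through the Chi-Square test or Fisher Exact test (if applicable"). For a quantitative variable in two independent samples: t-test or Mann-Whitney. For a numerical against a binary variable: AUC, with values above 0.75 read as high discrimination.
- **Methods for correlated data (Protocol 9.1):** repeated-measures analysis or GEE is assigned to the time effect. GEE is also assigned to clinical features as predictors of histologic features.
- **Size (Protocol 9.2):** "approximately 30 patients with MC are expected to be followed in the prospective component study".

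**The concern.** A patient can be active at month 3, in remission at month 9 and active again at month 15. Active and non-active records are therefore not two separate groups of patients, and a characteristic such as sex or smoking status is repeated unchanged across all of a patient's records. None of the methods that 9.1 offers for this comparison allows for that. The section does provide a method that would, but gives it to two different questions.

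An analyst who follows 9.1 has three routes:

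- pool the visits, which treats about 30 patients as about 240;
- test each visit, which gives every characteristic eight chances to reach significance;
- pick one visit, which leaves most of the follow-up unused.

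The first two can produce false predictors of disease activity. The third can miss real ones.

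**Working it through.** **1. The plan's own figures (9.2).** The half-width of a 95% interval is 1.96 × √(p(1−p)/300).
- p = 0.10: 1.96 × √(0.09/300) = 3.39%.
- p = 0.15: 1.96 × √(0.1275/300) = 4.04%.

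Both are below the stated 4.5%. The number of MC patients is 300 × 0.10 = 30 (300 × 0.15 = 45 at the upper prevalence). The plan's figures reproduce.

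**2. Inputs for the check.** From the protocol: 30 patients and 8 follow-up visits, so 30 × 8 = 240 records if all visits are attended. Assumed, because the protocol gives no value: two-sided level 0.05, 20-50% of records active, and the within-patient correlation, which is varied.

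**3. If visits were pooled.** For a characteristic fixed within patient, the design effect is DE = 1 + (8 − 1) × ICC, and the actual error rate is 2 × (1 − Φ(1.96/√DE)).

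| ICC | DE | Actual error rate |
|---|---|---|
| 0.05 | 1.35 | 9.2% |
| 0.1 | 1.70 | 13.3% |
| 0.3 | 3.10 | 26.6% |
| 0.5 | 4.50 | 35.6% |
| 0.55 | 4.85 | 37.3% |
| 0.7 | 5.90 | 42.0% |

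The number of patients does not enter the formula, so 45 patients instead of 30 would not reduce the inflation. Simulated pooled chi-square tests (10,000 runs per scenario, 30% or 50% active) agree: 12.9-13.7% at ICC 0.1, 35.4-36.2% at 0.5 and 42.7-43.7% at 0.7. A second simulation, with correlation of 0.3-0.7 set on a latent continuous scale, gives 17-35% for a pooled chi-square and 19-37% for a pooled t-test.

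**4. If significance at any of the eight visits were read as association.** With independent visits the chance of at least one false positive is 1 − 0.95⁸ = 33.7%. Simulated at ICC 0.1-0.5 it is 23-36% with chi-square and 9-27% with Fisher, which is conservative in samples this small. On the latent scale it is 12-26% for a binary trait and 28-32% for a continuous one.

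**5. If one visit, or one value per patient, were tested.** At a single visit the simulated error is 4.4-5.6% (chi-square) and 1.6-4.0% (Fisher). A t-test on each patient's number of active visits gives 4.6-5.3%. Neither is inflated.

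**6. What a single visit costs in power.** Take a true shift of 0.8 latent standard deviations, 30% active and latent correlation 0.5. A single-visit test has 37% power, and a patient-level analysis of all visits has 73%: 37/73 = 0.51, about half.

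**7. How the proposed model behaves.** In a simulation with 30 patients, eight visits, 30% active and correlation 0.3-0.7, bias-corrected logistic GEE rejected a true null in 3-4% of runs. Pooling rejected in 16-34% and any-visit Fisher in 18-20%. At the 0.8 SD shift, power was 56-81% for GEE against 29-34% for one visit.

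**The case against.** **The protocol does not prescribe a faulty analysis.** A reader might infer that repeated visits will be fed into independent-sample tests, so that 12-37% of null characteristics will be declared associated. The protocol does not support that. It nowhere says visits are pooled, and it restricts the t-test and Mann-Whitney test to independent samples. Where it does describe repeated activity, namely remission proportions and biomarker AUC, it works visit by visit. It sets no significance level and no rule that one significant visit is enough. This objection stands, and the error rates are therefore conditional.

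**AUC is also available.** Numerical characteristics such as age or BMI could be handled by AUC with a descriptive threshold rather than a p-value. The rejection rates for a continuous trait apply only if the t-test or Mann-Whitney test is used. This also stands, but it does not close the gap, because an AUC over pooled visits ignores clustering as well.

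**Two different error rates.** The pooled figure is the error of one test, while the any-visit figure is the chance of at least one error in eight tests. They happen to be similar in size, but they are not the same quantity.

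**Exploration, and detail for an analysis plan.** Section 2.3 predefines no hypothesis, the objective is to explore, and the choice of visit is often left to an SAP, which is not shown. This carries weight: an unnamed visit alone would not be worth raising. What remains is that 9.1 does allocate its methods, and it allocates the correlation-aware ones to other questions. An objective that spans 24 months is also poorly served by a single visit.

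**Conclusion.** The point holds as a misallocation of methods in 9.1, not as a demonstrated error rate. For characteristics against clinical activity, every method that fits the variable types treats records as independent, while the outcome is determined eight times in each of about 30 patients.

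- Under pooling or any-visit reading, the false-positive rate would be roughly 12-37% at an assumed two-sided 0.05 and moderate within-patient correlation. Outside that range, pooling gives about 9% at ICC 0.05 and about 43% at 0.7. Any-visit Fisher can be as low as 9% at ICC 0.1-0.5.
- Under a single-visit reading there is no inflation, but power is roughly half that of an analysis of all visits in the scenario examined.

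The pooled figures assume complete attendance; missed visits lower the design effect. The primary prevalence estimate is untouched, as is the MC versus non-MC comparison, where each patient counts once. The point does not extend to histological activity, which is assessed in follow-up only at month 24. Because the objective is secondary and exploratory, the change is advisable rather than essential.

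**What to change.** In 9.1, add one sentence for this 8.2 endpoint. Fit one logistic GEE per characteristic to active/non-active status at months 3 to 24, with the patient as cluster, visit and the characteristic as covariates, and small-sample-corrected standard errors. Alternatively, name in advance one summary per patient, such as the proportion of visits with active disease. Either way, report one estimate with a 95% confidence interval per characteristic. For characteristics recorded at every visit, such as laboratory values and therapies, say whether the baseline or the same-visit value is used.

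Keep chi-square/Fisher, t and Mann-Whitney for the cross-sectional comparison of MC with non-MC patients.

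The cost is wording and slightly more analysis work. GEE is already a planned method and no further data are needed. The corrected GEE is somewhat conservative with about 30 clusters (3-4% against a nominal 5% in the simulation above).
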